5.3.3. Graphical Displays

The time to onset of the first occurrence of SARS-CoV-2 COVID-19 will be graphically summarized using Kaplan-Meier methods for the PPE analysis set, seronegative subjects only with onset at least 14 days after last vaccination for each cohort.

- These graphs will be prepared regardless of severity according to the case definitions mild, moderate, severe and US FDA harmonized and for asymptomatic/undetected case definition.

5.4. Other Analyses

5.4.1. Definition of Subgroups

Selected descriptive statistics will be provided by vaccination dose groups in each cohort for the following subgroups:

- sex
- age group (18 - ≤ 59 & ≥ 60 years)
- presence of baseline comorbidity (yes/no)
- sites
- higher geographical region (West; Midwest; Northeast and South): Categorization of regions by pooling of US states as are described in [Table 3](#) (based on U.S. Department of Commerce Economics and Statistics Administration U.S. Census Bureau).

Table 3: Geographical Regions

CTMS Site #	City, State	Region
PPD	North Charleston, SC	South
	Peoria, IL	Midwest
	Houston, TX	South
	Rochester, NY	Northeast
	Lenexa, KS	Midwest
	Lexington, KY	South
	Long Beach, CA	West
	Mount Pleasant, SC	South
	Tucson, AZ	West
	Phoenix, AZ	West
	Metairie, LA	South
	Hallandale Beach, FL	South
	Hollywood, FL	South
	Boston, MA	Northeast
	The Villages, FL	South
	Orlando, FL	South
	Anaheim, CA	West
	West Jordan, UT	West
	N. Hollywood, CA	West
	Denver, CO	West
	Anderson, SC	South
	Boston, MA	Northeast

Analysis Methods:

Descriptive analyses/summary will be provided for PPE analysis set for each cohort by dose groups. These analyses may include but are not limited to:

- The number and percentage of severity of SARS-CoV-2 COVID-19 cases
- Number of events and follow-up time for SARS-CoV-2 COVID-19 cases by subgroups
- Based on availability of the data, for COVID-19 requiring medical intervention/ hospitalization, a summary table will be provided by type of intervention (as indicated by the adjudicators, if available) with onset at least 14 days post last vaccination. A severity adjusted analysis will be done on the medical intervention endpoint (such as composite endpoint of hospitalization, ICU admission, mechanical ventilation, and ECMO, linked to objective measures such as decreased oxygenation, X-ray or CT findings

5.4.2. Symptoms of Infection with Coronavirus-19 (SIC)

The SIC is a disease-specific patient-reported outcome (PRO) instrument that is completed by the participant, self-administered. The SIC has a total of 30 items assessing signs and symptoms of COVID-19. The first 25 items, the participant indicates “yes” or “no” if they have a symptom and if “yes” report a severity from 0 (none) to 10 (worst possible). The second part has the participant enter their temperature, and the third part has the participant record “yes” or “no” (absence or presence of additional signs and symptoms). The analyses are conducted by part 1, part 2 and part 3, scored separately for PPE analysis set.

SIC Analysis:

- Part 1 (25 symptoms): Each symptom is present or absent (0), and if present rated on a 10 point scale from ranging from 0 (None) to 10 (Worst possible).

The **symptom score** is the mean score of all items on the SIC for each day, during the COVID-19 episode.

The **symptom duration** is the period from the first day of symptoms till the last day with symptoms in Days (calculated as last day with symptoms – first day of symptoms + 1).

The **symptom area under the curve (AUC)** is the area under the curve for the complete COVID-19 episode.

The **peak symptom score** is the maximum of all the symptom scores during the COVID-19 episode.

- Part 2: Fever/ temperature:

Fever will be scored (fever score) as the maximum recorded temperature for each day during the COVID-19 episode.

Fever will be coded as ‘Present’ if the fever score is $\geq 38.0^{\circ}\text{C}$ or $\geq 100.4^{\circ}\text{F}$ and ‘Absent’ otherwise.

The **total fever days** is the number of days with fever present during the COVID-19 episode.

Fever duration will be the period from the first day with fever till the last day with fever in Days (calculated as last day with fever – first day of fever + 1).

The **peak fever** is the maximum fever score during the COVID-19 episode.

The **fever AUC** is the AUC of fever score during the total of fever days of the COVID-19 episode. (For the AUC if there is a single missing day between days with fever the missing day will be ignored, i.e., interpolation will be used in the calculation of the AUC.)

The fever score will also be coded using FDA grades for fever.

Part 3: Each of the 3 specific symptoms is either present (1) or absent (2).

The **specific symptom score** is the mean of all scores during the COVID-19 episode.

The **specific symptom duration** is the duration of specific symptoms during the COVID-19 episode from the first day with a specific symptom till the last day with a specific symptom in Days (calculated as last day with a specific symptom – first day of a specific symptom + 1).

The **total specific reported symptom score** is the mean of all scores during the COVID-19 episode at which a subject has reported at least one specific symptom.

Note 1: For Part 1, total scores will be calculated based on the number of assessments completed by the participant per day and in cases where more than 75% of the items needed to calculate the score is not collected (reported as no answer to the part 1 Yes/No possibility AND no severity rate), then the value for that score will be set to missing. For example, if a participant has responded to 7 or more out of the 25 symptom scale questions the score will be the mean of the available questions. If the participant has only completed 6 or less of the questions then the symptom score will be set to missing, unless a subject has only provided responses ‘Yes’ to all of the answered questions (then it is assumed that the subject only noted the pertinent symptoms for that day). In case of missing severity rate and the answer was ‘yes’ the rate will be imputed by ‘5’.

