- **Resolution of an episode:** Resolution of the COVID-19 episode is defined as having 2 consecutive SARS-CoV-2 negative nasal swabs and 2 consecutive days with no COVID-19-related signs or symptoms. [The date taken will be the first of the 2 consecutive negative swabs, OR the first day with no COVID-19 related signs or symptoms, whichever comes last. For this determination, all sources of information will be used (eCOA, eCRF or an AE linked to COVID-19). In case of missing days, it will depend on if those are before or after the first day of the two consecutive SARS-CoV-2 negative nasal swabs. If before days with missing data have no consequence. If after, it is assumed that if days with missing data are after a day with no symptoms, the subsequent days also were without symptoms. If days with missing data are after a Day with symptoms, the assumption depends on the data of subsequent Days. If there are no more than 2 Days without data and the next Day does have (at least mild) symptoms, the missing days will be assumed to also have had symptoms. In all other cases it will be assumed that days with missing data were without symptoms and the rule to determine the resolution of symptoms will be applied.]
- **Molecularly confirmed case:** Events for which at least one SARS-CoV-2 PCR positive test was obtained by the nasal swab PCR test.
- **A suspected COVID-19 case** is a case which meets any of the symptomatic COVID-19 definitions according to the CSAC without a documented PCR positive result (any source) or a positive serology test.

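### SIC symptom, fever and specific-symptom durations have no rule for a participant still symptomatic at the last diary entry, so a truncated record counts as a completed, shorter duration

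*SAP*

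**What the plan says.** The supplemental SAP, section 5.4.2, describes the SIC as a "patient-reported outcome (PRO) instrument that is completed by the participant, self-administered". It then defines three durations with one construction:

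- Part 1: symptom duration "is the period from the first day of symptoms till the last day with symptoms in Days", and is "calculated as last day with symptoms – first day of symptoms + 1".
- Part 2, fever duration: "calculated as last day with fever – first day of fever + 1".
- Part 3, specific-symptom duration: "calculated as last day with a specific symptom – first day of a specific symptom + 1".

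Part 2 also defines total fever days, which "is the number of days with fever present during the COVID-19 episode". A day's fever is present at or above 38.0°C and absent in every other case.

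The section has two missing-data rules, and neither concerns duration. One sets the Part 1 daily score to missing when more than 75% of its items are missing. The other is limited to the fever AUC: "For the AUC if there is a single missing day between days with fever the missing day will be ignored".

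Section 5.2.2 has a separate rule for missing days when the resolution date of an episode is set. It ends with "In all other cases it will be assumed that days with missing data were without symptoms". That rule draws on the eCOA, the eCRF and AEs linked to COVID-19, and resolution also requires two consecutive negative swabs.

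**The concern.** The formula does not distinguish between symptoms that ended and a diary that ended. A participant may stop completing the SIC while still ill, for example on admission to hospital, on withdrawal or at database cut-off. The last recorded symptomatic day then becomes the end of the illness. Statistically this is a right-censored duration entered as an observed one.

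At stake is the description of how long illness lasts in each cohort and dose group. Means and medians would be too low, and groups could differ through diary completion alone. Longer illnesses leave more days on which a diary can stop, so contrasts between longer and shorter illness would shrink.

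A smaller gap of the same kind affects fever. Read literally, a day with no recorded temperature falls under absent, which lowers total fever days and can shorten fever duration when the unrecorded day was the last with fever.

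**Working it through.** **No plan figure to reproduce.** The SAP gives no figure for SIC duration, diary completion or diary stopping. All inputs below other than the duration formula are assumptions.

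**1. Direction.** Let D be the true duration and L the last diary day, both counted from onset. With daily entries up to L, the formula scores min(D, L), which cannot exceed D. The error is therefore downward only.

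**2. Worked case (assumed).** A participant is ill on days 1 to 14 and the diary stops after day 5.
- Formula in section 5.4.2: 5 − 1 + 1 = 5 days, counted as complete.
- True duration: 14 − 1 + 1 = 14 days.
- With censoring, the record would read at least 5 days, ongoing.

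**3. Size under constant stopping.** Assume D is a gamma variable with mean 10 days, rounded up (true mean about 10.5), and a daily stopping chance p that is the same for everyone. Then

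scored mean = Σ P(D ≥ k) × (1 − p)^(k−1), over k = 1, 2, …

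Understatement = 1 − scored mean / true mean.

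| p per day | Gamma shape | True mean | Scored mean | Understated by | Stop while ill |
|---|---|---|---|---|---|
| 2% | 1 | 10.51 | 8.83 | 16% | 16% |
| 2% | 4 | 10.50 | 9.36 | 11% | 17% |
| 3% | 1 | 10.51 | 8.18 | 22% | 22% |
| 3% | 4 | 10.50 | 8.85 | 16% | 24% |
| 5% | 1 | 10.51 | 7.12 | 32% | 32% |
| 5% | 4 | 10.50 | 7.97 | 24% | 37% |

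Shape 2 lies between these rows.

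**4. Longer against shorter illness, same stopping rate.** Shape 4, true means 7.5 and 14.5 days:

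| p per day | 7.5 days scored as | Understated by | 14.5 days scored as | Understated by |
|---|---|---|---|---|
| 2% | 6.92 | 8% | 12.34 | 15% |
| 3% | 6.66 | 11% | 11.44 | 21% |
| 5% | 6.18 | 18% | 9.93 | 32% |

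The longer illness loses nearly twice the proportion. The true gap is 14.5 − 7.5 = 7.0 days. At 5% the scored gap is 9.93 − 6.18 = 3.75 days. The order does not change.

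**5. What a reversal would need.** Assume true means of 7.0 days (milder, no diary stops) and 14.0 days (sicker), with a share s of sicker diaries stopping on day 3 to 7. The sicker group's scored mean is 13.1 days at s = 10%, 11.3 at 30%, 9.5 at 50%, 7.6 at 70% and 5.8 at 90%. If every sicker diary stops, it is 4.9. The scored mean is linear in s, so it equals 7.0 when 14.0 − s × (14.0 − 4.9) = 7.0, that is s = 7.0 / 9.1 = 77%.

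**The case against.** **The measures carry little weight.** They sit under other analyses in an exploratory supplemental SAP. They feed no hypothesis test, relative vaccine efficacy estimate or case classification. Severity is decided by the adjudication committee, and output detail is left to a specification document that is not shown. This stands and limits the importance of the point. It does not supply the missing rule, because the SAP itself fixes the formula.

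**The sickest cases need not look shortest.** A reader might infer that severe cases will appear shorter than moderate ones. The documents do not support this. Constant stopping preserves the order, and a reversal in the assumed example needs about three quarters or more of the sicker diaries to stop early while no milder diary does. The SAP has no data on stopping by severity.

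**Section 5.2.2 does not score such a participant as recovered.** Its symptom-free assumption governs the episode resolution date. It applies only to missing days after the first of the two negative swabs; earlier missing days have no consequence. Section 5.4.2 assigns no recovery status. This objection stands: the point rests on the formulas in section 5.4.2 alone.

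**The symptom AUC is not shown to be cut off in the same way.** It is defined over the complete episode. How missing days enter it is not stated, but truncation at the last symptom day is not prescribed.

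**Kaplan-Meier estimation has its own limits.** It assumes that stopping is unrelated to the remaining duration. Splitting by 2 cohorts, 3 doses and 3 severity levels gives 2 × 3 × 3 = 18 cells, in a plan that runs efficacy analyses from 6 cases. Both objections stand and narrow the fix.

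**Conclusion.** The point holds in limited form. Followed as written, the three SIC duration formulas count an illness whose diary stopped early as a completed, shorter one, and nothing in section 5.4.2 prevents this. The direction is certain. The size is not: the range of roughly 11% to 32% rests entirely on an assumed true mean near 10.5 days, gamma shapes 1 to 4 and a constant daily stopping chance of 2% to 5%. If few diaries stop early, the effect is small. What follows is understated durations and, under equal stopping, compressed differences between longer and shorter illnesses. The consequence is confined to descriptive, exploratory summaries.

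**What to change.** In section 5.4.2:

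- Take the last day with symptoms, fever or a specific symptom from all sources already collected (eCOA, eCRF, AEs linked to COVID-19), where the source records that symptom or fever.
- If the participant is still symptomatic at the last available record, flag the duration as ongoing and right-censor it at that record.
- Report the number censored per cohort and dose group.
- Summarise duration by Kaplan-Meier median by cohort and dose group, and by severity only where case numbers allow. State that stopping may be informative.
- Code a day with no recorded temperature as missing, not as fever absent.

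The cost is a few lines of SAP text and one flag derived from existing dates. Section 5.3.3 already uses Kaplan-Meier methods for time to onset. The downside is that some medians may not be reached. Censoring also does not fully remove the bias if sicker participants are the ones who stop their diaries, which is why the censored counts should be shown beside the medians.

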6.10. Appendix 10 Toxicity Grading Scale

Adapted from the FDA Guidance document “Toxicity Grading Scale for Healthy Adult and Adolescent Volunteers Enrolled in Preventive Vaccine Clinical Trials” (September 2007) (US DHHS 2007).

A: Tables for Clinical Abnormalities

Local Reaction to Injectable Product	Mild (Grade 1)	Moderate (Grade 2)	Severe (Grade 3)	Potentially Life Threatening (Grade 4)
Pain/Tenderness [#]	Aware of symptoms but easily tolerated; Does not interfere with activity; Discomfort only to touch	Notable symptoms; Requires modification in activity or use of medications; Discomfort with movement	Incapacitating symptoms; Inability to do work, school, or usual activities; Use of narcotic pain reliever	Hospitalization; Pain/tenderness causing inability to perform basic self-care function
Erythema [#]	25 – 50 mm	51 – 100 mm	> 100 mm	Hospitalization; Necrosis or exfoliative dermatitis
Swelling [#]	25 – 50 mm	51 – 100 mm	> 100 mm	Hospitalization; Necrosis

[#] Revised by the sponsor.

Vital Signs *	Mild (Grade 1)	Moderate (Grade 2)	Severe (Grade 3)	Potentially Life Threatening (Grade 4)
Fever (°C) ** (°F)***	38.0 - 38.4 100.4 - 101.1	38.5 - 38.9 101.2 - 102.0	39.0 - 40.0 102.1 - 104.0	> 40 > 104.0
Tachycardia - beats per minute	101 – 115	116 – 130	> 130	Hospitalization for arrhythmia [#]
Bradycardia - beats per minute***	50 – 54	45 – 49	< 45	Hospitalization for arrhythmia [#]
Hypertension (systolic) - mm Hg	141 – 150	151 – 155	> 155	Hospitalization for malignant hypertension [#]
Hypertension (diastolic) - mm Hg	91 – 95	96 – 100	> 100	Hospitalization for malignant hypertension [#]
Hypotension (systolic) – mm Hg	85 – 89	80 – 84	< 80	Hospitalization for hypotensive shock [#]
Respiratory Rate – breaths per minute	17 – 20	21 – 25	> 25	Intubation

* Participant should be at rest for all vital sign measurements.

** For oral temperature: no recent hot or cold beverages or smoking.

*** When resting heart rate is between 60 – 100 beats per minute. Use clinical judgment when characterizing bradycardia among some healthy participant populations, for example, conditioned athletes.

[#] Revised by the sponsor.

Systemic (General)	Mild (Grade 1)	Moderate (Grade 2)	Severe (Grade 3)	Potentially Life Threatening (Grade 4)
Vomiting [#]	No interference with activity or 1 – 2 episodes/24 hours	Some interference with activity or > 2 episodes/24 hours	Prevents daily activity, requires outpatient IV hydration	Hospitalization; Hypotensive shock

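### Fever AUC integrates absolute temperature with no reference level subtracted, so it is dominated by the number of fever days and says little about how high the fever was

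*SAP*

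**What the plan says.** All of the definitions are in the supplemental SAP, section 5.4.2, Part 2.

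- Height of the curve: "Fever will be scored (fever score) as the maximum recorded temperature for each day during the COVID-19 episode". This is a temperature on the absolute scale.
- Fever day: "Fever will be coded as ‘Present’ if the fever score is" at or above 38.0 °C (100.4 °F).
- Fever AUC: it "is the AUC of fever score during the total of fever days of the COVID-19 episode". No baseline, threshold or other reference is taken off, and nothing elsewhere in the SAP defines another height.
- Missing data: if one day is missing between fever days, "the missing day will be ignored, i.e., interpolation will be used in the calculation of the AUC". This is the only indication of the integration rule.
- Companion measures: total fever days "is the number of days with fever present during the COVID-19 episode"; fever duration is "calculated as last day with fever – first day of fever + 1"; peak fever is the largest fever score in the episode; and the score is also coded by FDA grade.

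The grading table in the main SAP (section 6.10, Appendix 10) gives Grade 1 fever as "38.0 - 38.4 100.4 - 101.1" (°C, then °F). It puts 40.0 °C at the top of Grade 3.

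**The concern.** An area under a curve is worth adding to a peak and a duration only if it combines the two. That requires a scale whose zero means absence of the thing measured. The Part 1 symptom score has such a zero (0 is none). Body temperature in °C or °F does not: on a fever day at least 38 of the roughly 38 to 40 units are the same for everyone, and only the last few tenths to two degrees carry information about intensity. The area is then close to a constant multiplied by the number of days, which two other parameters already report.

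If fever AUC is tabulated under that name, a reader may take it as a summary of fever burden when it is essentially a rescaled day count. The unnamed integration rule adds a smaller problem, because the value for a one-day fever depends on which rule the programmer picks.

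**Working it through.** The SAP gives no numerical value for fever AUC, so there is no planned figure to reproduce. The check applies the definition to simple episodes.

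**Inputs.** Fever-day minimum 38.0 °C (section 5.4.2). Grade 1 range 38.0 to 38.4 °C and top of Grade 3 40.0 °C (main SAP, section 6.10). Daily readings, so the step is 1 day.

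**Formulas for a constant temperature T over n consecutive fever days.**
- Trapezoid through daily points: AUC = (n − 1) × T
- Daily sum, each day one day wide: AUC = n × T

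**As defined.**

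| Episode | Trapezoid | Daily sum |
|---|---|---|
| 3 days at 38.0 °C | 2 × 38.0 = 76 | 3 × 38.0 = 114 |
| 3 days at 38.4 °C | 2 × 38.4 = 76.8 | 3 × 38.4 = 115.2 |
| 2 days at 40.0 °C | 1 × 40.0 = 40 | 2 × 40.0 = 80 |
| 1 day at 40.0 °C | 0 | 40 |

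For the 3-day fever at 38.0 °C against the 2-day fever at 40.0 °C, the ratio is 76/40 = 1.90 under the trapezoid and 114/80 = 1.43 under the daily sum.

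**Effect of height at fixed duration.** 40/38 − 1 = 5.3%, under either rule.

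**How long one extra day outweighs 2 °C.** A 38 °C fever of D + 1 days outscores a 40 °C fever of D days when:
- trapezoid: 38D > 40(D − 1), that is D < 20, so for D up to 19 days;
- daily sum: 38(D + 1) > 40D, that is D < 19, so for D up to 18 days.

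**Share of variation.** In 20,000 simulated episodes (assumption: 1 to 7 consecutive fever days, temperatures uniform between 38 and 40 °C), R² of AUC on the number of fever days was above 0.999 with the trapezoid and above 0.998 with the daily sum. R² on temperature was below 0.001 under both.

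**Arbitrary zero.** In °F the trapezoid gives 2 × 100.4 = 200.8 against 1 × 104.0 = 104.0, a ratio of 1.93 instead of 1.90. The comparison between the same two episodes changes with the unit.

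**Gaps.** Fever at 38.5 °C on days 1 and 3 only gives 2 × 38.5 = 77.0 if the trapezoid runs over calendar days and 38.5 if the two fever days are joined. The text covers a missing day in the gap, but not a day recorded without fever.

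**With a reference subtracted and each fever day one day wide.**

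| Reference | 3 days at 38.0 °C | 2 days at 40.0 °C | 1 day at 40.0 °C |
|---|---|---|---|
| 37.0 °C | 3 × 1.0 = 3.0 | 2 × 3.0 = 6.0 | 3.0 |
| 37.5 °C | 3 × 0.5 = 1.5 | 2 × 2.5 = 5.0 | 2.5 |
| 38.0 °C | 3 × 0 = 0 | 2 × 2.0 = 4.0 | 2.0 |

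The order of the first two episodes reverses at all three references. Subtraction alone, under a trapezoid, also reverses it (reference 37.0 °C: 2.0 against 3.0; 38.0 °C: 0 against 2.0), but leaves the one-day fever at 0. The unit-width day is what removes the zero.

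**The case against.** Several stronger readings are tempting, and the document does not carry them.

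- A reader might infer that the longer mild fever always scores about twice the short high one and that a one-day fever always scores zero. Both need the trapezoid. The interpolation note fits that rule but does not name it, and a daily sum with the missing value interpolated is also possible. The duration formula counts one fever day as one day, which leans that way. Under the daily sum the ratio is 1.43 and the one-day fever scores 40. This objection stands, and both statements must stay conditional.
- A reader might infer that the AUC contains nothing but duration. Height does contribute, by up to about 5% between 38 and 40 °C. It is dominated by duration, not identical to it.
- A reader might infer that comparisons between dose groups or severity classes will mislead. The SAP specifies no test, model or contrast on fever AUC. It is in none of Estimands 1 to 5, and the AUC plotted against viral load in section 5.4.4 is the symptom AUC. High fevers are not hidden, since peak fever and FDA grade report them.
- The SAP does not say that the AUC is meant to weigh height against duration, so calling its order of the two examples wrong presupposes a purpose. That is fair, and the example does contrast extremes. The near redundancy with the day count does not depend on that premise.
- The 37.5 °C reference comes from the temperature intervals for safety tabulation in the main SAP (section 5.6.3.2), not from a definition of fever burden. That is also true. The choice is a convention, but the reversal in the example does not depend on it.

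**Conclusion.** The point holds as a minor one. As written, fever AUC is the area under absolute temperature, so each fever day contributes about 38 to 40 units and 2 °C of fever height changes the value by about 5%. This follows from a stated definition and holds under either integration rule. Three days at 38.0 °C outscore two days at 40.0 °C by a factor of 1.90 (trapezoid) or 1.43 (daily sum).

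The zero for a one-day fever, whose fever duration is 1 day, follows only if the implied trapezoid is used. The R² figures rest on the assumed episode lengths and temperatures; the 5% figure does not.

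The consequence is confined to one descriptive, exploratory parameter that adds almost nothing to total fever days and should not be read as fever burden. No efficacy estimate is affected.

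**What to change.** In the supplemental SAP, section 5.4.2, Part 2, define fever AUC as the sum over fever days of (daily maximum temperature in °C minus a pre-stated reference, for example 37.5 °C). Count each fever day as one day wide, and give a single missing day between fever days its interpolated value. Convert all readings to °C first.

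This settles the height, the integration rule, the one-day fever and the gap together. For fever at 38.5 °C on days 1 and 3, the result is 2 × 1.0 = 2.0 °C-days if day 2 was recorded without fever and 3 × 1.0 = 3.0 if day 2 is missing and interpolated.

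The cost is one sentence of SAP text and one change to a derived variable. The downside is that the reference level is a convention: it should be fixed before the variable is derived and stated in the table footnote.
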